# 1. BACKGROUND AND DESIGN

The trial hypothesis under investigation is that treatment with aspirin is safe and improves important surrogate clinical outcomes in adult patients with ARDS.

The objective of the trial is

1. To conduct a prospective randomised, double-blind, allocation concealed, placebo-controlled phase 2 trial of aspirin as a treatment for ARDS.
2. To study the biological effects of aspirin on pulmonary and systemic
  - a. inflammatory responses,
  - b. epithelial and endothelial function and injury and
  - c. lipid inflammatory mediators

Subjects will be randomised to receive aspirin 75mg capsule or a placebo capsule enterally for up to 14 days. Subjects will be randomised in a 1:1 ratio using blocks of variable size. The first dose of the study drug will ideally be administered within 4 hours of randomisation and subsequent doses will be as close to 10 am as possible starting on the following calendar day.

Patients will be eligible to participate in the study if they fulfil the following criteria:

## **Inclusion criteria:**

1. Patients receiving invasive mechanical ventilation.
2. ARDS as defined by the Berlin definition.
  - a. Onset within 1 week of identified insult.
  - b. Within the same 24 hour time period
    - i. Hypoxic respiratory failure ( $\text{PaO}_2/\text{FiO}_2$  ratio  $\leq 40\text{kPa}$  on  $\text{PEEP} \geq 5\text{ cmH}_2\text{O}$ )
    - ii. Bilateral infiltrates on chest X-ray consistent with pulmonary oedema not explained by another pulmonary pathology
    - iii. No evidence of heart failure or volume overload

The time of onset of ARDS is when the last ARDS criterion is met.

[figure not shown]
## **Exclusion criteria:**

1. More than 72 hours from the onset of ARDS.

2. Age < 16 years.
3. Patient is known to be pregnant.
4. Participation in a clinical trial of an investigational medicinal product within 30 days.
5. Current treatment with aspirin or within the past 4 weeks.
6. Platelet count <  $50 \times 10^9/l$ .
7. Haemophilia or other haemorrhagic disorder or concurrent therapeutic anticoagulant therapy.
8. History of aspirin sensitive asthma or nasal polyps associated with asthma.
9. Active or history of recurrent peptic ulcer and/ or gastric/ intestinal haemorrhage or other kinds of bleeding such as cerebrovascular haemorrhage.
10. Traumatic brain injury.
11. Active gout.
12. Currently receiving methotrexate.
13. Severe chronic liver disease with Child-Pugh score > 12.
14. Known hypersensitivity or previous adverse reaction to salicylic acid compounds or prostaglandin synthetase inhibitors.
15. Physician decision that aspirin is required for proven indication.
16. Contraindication to enteral drug administration, e.g. patients with mechanical bowel obstruction.
17. Treatment withdrawal imminent within 24 hours.
18. Consent declined.

The trial is summarised in Figure 1.

**Figure 1. Trial schematic diagram**

Full details of the background to the trial and its design are presented in the protocol.

## **2. OUTCOME MEASURES**

As this is a phase 2 clinical study, several outcomes will be evaluated to determine whether treatment with aspirin shows efficacy for important surrogate clinical outcomes.

### **2.1 Primary outcome measure**

The primary outcome measures OI at day 7. OI is a physiological index of the severity of ARDS and measures both impaired oxygenation and the amount of mechanical ventilation delivered. We and others have shown OI is independently predictive of mortality in patients with ARDS. We have chosen day 7 as we expect this time interval will minimise the competing effects of death and extubation, while allowing a sufficient time interval for a biological effect to occur.

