### **2.2 Secondary outcome measures**

The following secondary clinical outcomes will also be assessed:

1. OI at days 4 and 14
2. Physiological indices of ARDS, as measured by respiratory compliance (CRs) and P/F ratio on days 4, 7 and 14
3. Organ failure as measured by change in sequential organ failure assessment (SOFA) score from baseline to days 4, 7 and 14
4. Safety and tolerability as assessed by the occurrence of adverse events/reactions (AE/AR), serious adverse events/reactions (SAE/SAR) and suspected unexpected serious adverse reactions (SUSAR).

Outcomes will be measured at baseline and daily up to day 14 or until the patient is discharged from ICU or the patient dies. Although duration of ventilation, ventilation free days at day 28 and 28 and 90-day mortality as well as length of ICU stay will be recorded, these important clinical outcomes are not included as major outcome measures as the study is not adequately powered to assess these outcomes.

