## 4. DEFINITION OF TERMS

Term	Definition
Vasopressors	Vasopressors are defined as any inotropic/vasopressor agent except dopamine < 6mcg/kg/min.
SAP II	New Simplified Acute Physiology Score
Murray Lung Injury Score	Scoring system using radiology, PF ratio, PEEP and respiratory compliance to assess the extent of adult lung injury.
APACHE II score	Acute Physiology and Chronic Health Evaluation II score. A disease severity classification system.
Predicted Body Weight (Kg)	$PredictedBodyWeight = \begin{cases} 50 + 0.91 * (Height - 152.4) & \text{for Male} \\ 45.5 + 0.91 * (Height - 152.4) & \text{for Female} \end{cases}$
Oxygenation Index (cmH 2 O/kPa)	$OI = \frac{(MAP * FiO_2)}{PaO_2} * 100$
Total SOFA Score	Guideline 13: SOFA Score v1.0 Final 04/02/2016
Respiratory Compliance (ml/cmH 2 O)	$RespiratoryCompliance = \frac{TidalVolume}{[PlateauPressure - PEEP]}$
PF ratio (kPa)	$PFRatio = \frac{PaO_2}{FiO_2}$
Unassisted breathing	Unassisted breathing is defined as; extubated with supplemental oxygen, or room air, or open T-tube breathing, or tracheostomy mask breathing, or CPAP ≤ 5 cm H 2 O without pressure support for a calendar day. Patients receiving pressure support via non-invasive ventilation will be defined as

	receiving ventilatory support. The date recorded will be the first calendar day of the final period of ventilation free days
Ventilator free days (VFDs)	
The number of days alive and free from ventilation between final successful weaning and day 28 after study enrolment.
 $VFD = \begin{cases} (28 - x), & \text{if patient alive at day 28} \wedge x \leq 27 \\ 0, & \text{if patient died within 28 days} \vee x > 27 \end{cases}$ 
Where x is number of days until patient achieved unassisted breathing

Duration of ventilation (days)	
Duration of ventilation
 $= \begin{cases} \text{Date of unassisted breathing} - \text{Date of randomisation, if the patient achieved unassisted breathing} \\ \text{Date of death} - \text{Date of randomisation, if the patient died prior} \end{cases}$ 
This calculation will be censored at day 90.

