## 6. ANALYSIS PRINCIPLES

Primary outcome measure is the OI at day 7. Unadjusted (primary analysis) and adjusted analysis will be carried out to test whether there is a statistically significant difference between the aspirin & placebo groups. Secondary analysis will be carried out, if the day 7 OI values are missing, using last value carry forward method.

Secondary outcome measures are OI, CRs, PF ratio, and SOFA score at day 4, 7, 14 and safety. Unadjusted and adjusted analysis will be carried out on OI, CRs, PF ratio, SOFA score, to test whether there is a statistically significant difference between the groups.

Unadjusted analysis will be carried out using Independent sample t-test. Adjusted analysis will be carried out using ANCOVA or [mixed modelling technique](#), based the number of data points available at each time point. Estimates & 95% confidence interval will be reported.

The number of AE, ARs, SAE, SARs, SUSARs and number (%) of patient experiencing the events will be reported. Fisher's exact test and proportion test will be used to check whether incidences of adverse events differ between the groups. Relative risk and 95% CI will be reported.

Exploratory analysis on mediators will be carried out using student t-tests or non-parametric alternative and Fishers Exact Test, presented by day where applicable. The estimates & 95% CIs will be reported. Statistical diagnostic methods will be used to check for violations of the assumptions, and transformations will be performed if required. For binary outcome measures, risk ratios and associated 95% CI will be calculated. Survival analysis technique will be used for time-to-event data. Median survival time & 95% CI will be estimated using Kaplan-Meier estimation method and the Kaplan-Meier plots will be presented. In all time-to-event analyses, patients that did not experience the event in question (e.g. death) were censored on the date last seen or 90 days. The equality of survivorship function of aspirin & placebo group will be tested

for significance using a log-rank  $\chi^2$  test. Hazard ratios (HRs) & 95% CIs will be reported if the proportionality assumption holds.

Correlations between changes in the biological markers measured and physiological and clinical outcomes will be assessed by appropriate graphical and statistical methods including Pearson's (or Spearman's) correlation coefficient.

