A secondary analysis excluding patients identified to have aspirin resistance will also be undertaken.

Analyses will be conducted according to intention to treat principle. All statistical tests will be 2-sided and a p-value of 0.05 will be considered as statistically significant, unless adjustment for multiple testing was needed. A single analysis is planned at the end of the trial. Every effort will be made to minimise missing baseline and outcome data in this trial. Any ad-hoc analysis will be reported as per the regulatory requirement.

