**Table A3. Main Clinical Outcome Variables: PF Ratio, Oxygenation Index, SOFA, Respiratory Compliance at each visit**

	Unadjusted, Mean $\pm$ SD			Mean Difference (95% CI)	p-value	Adjusted, Mean $\pm$ SE		Mean Difference (95% CI)	p-value
	All patients	Aspirin	Placebo			Aspirin	Placebo		
Primary outcome; OI at day 7									
Observed values (n=<n>)	xx.x $\pm$ x.x	xx.x $\pm$ x.x	xx.x $\pm$ x.x	xx.x (xx.x to xx.x)	0.xxx	xx.x $\pm$ x.x	xx.x $\pm$ x.x	xx.x (xx.x to xx.x)	0.xxx
Imputed values(n=<n>)*	xx.x $\pm$ x.x	xx.x $\pm$ x.x	xx.x $\pm$ x.x	xx.x (xx.x to xx.x)	0.xxx	xx.x $\pm$ x.x	xx.x $\pm$ x.x	xx.x (xx.x to xx.x)	0.xxx
Oxygenation Index									
Baseline (n=<n>)	xx.x $\pm$ x.x	xx.x $\pm$ x.x	xx.x $\pm$ x.x	xx.x (xx.x to xx.x)	0.xxx				
Day 4 (n=<n>)	xx.x $\pm$ x.x	xx.x $\pm$ x.x	xx.x $\pm$ x.x	xx.x (xx.x to xx.x)	0.xxx	xx.x $\pm$ x.x	xx.x $\pm$ x.x	xx.x (xx.x to xx.x)	0.xxx
Day 14 (n=<n>)	xx.x $\pm$ x.x	xx.x $\pm$ x.x	xx.x $\pm$ x.x	xx.x (xx.x to xx.x)	0.xxx	xx.x $\pm$ x.x	xx.x $\pm$ x.x	xx.x (xx.x to xx.x)	0.xxx
Respiratory compliance									
Baseline (n=<n>)	xx.x $\pm$ x.x	xx.x $\pm$ x.x	xx.x $\pm$ x.x	xx.x (xx.x to xx.x)	0.xxx				
Day 4 (n=<n>)	xx.x $\pm$ x.x	xx.x $\pm$ x.x	xx.x $\pm$ x.x	xx.x (xx.x to xx.x)	0.xxx	xx.x $\pm$ x.x	xx.x $\pm$ x.x	xx.x (xx.x to xx.x)	0.xxx
Day 7 (n=<n>)	xx.x $\pm$ x.x	xx.x $\pm$ x.x	xx.x $\pm$ x.x	xx.x (xx.x to xx.x)	0.xxx	xx.x $\pm$ x.x	xx.x $\pm$ x.x	xx.x (xx.x to xx.x)	0.xxx
Day 14 (n=<n>)	xx.x $\pm$ x.x	xx.x $\pm$ x.x	xx.x $\pm$ x.x	xx.x (xx.x to xx.x)	0.xxx	xx.x $\pm$ x.x	xx.x $\pm$ x.x	xx.x (xx.x to xx.x)	0.xxx
PF ratio									
Baseline (n=<n>)	xx.x $\pm$ x.x	xx.x $\pm$ x.x	xx.x $\pm$ x.x	xx.x (xx.x to xx.x)	0.xxx				
Day 4 (n=<n>)	xx.x $\pm$ x.x	xx.x $\pm$ x.x	xx.x $\pm$ x.x	xx.x (xx.x to xx.x)	0.xxx	xx.x $\pm$ x.x	xx.x $\pm$ x.x	xx.x (xx.x to xx.x)	0.xxx
Day 7 (n=<n>)	xx.x $\pm$ x.x	xx.x $\pm$ x.x	xx.x $\pm$ x.x	xx.x (xx.x to xx.x)	0.xxx	xx.x $\pm$ x.x	xx.x $\pm$ x.x	xx.x (xx.x to xx.x)	0.xxx
Day 14 (n=<n>)	xx.x $\pm$ x.x	xx.x $\pm$ x.x	xx.x $\pm$ x.x	xx.x (xx.x to xx.x)	0.xxx	xx.x $\pm$ x.x	xx.x $\pm$ x.x	xx.x (xx.x to xx.x)	0.xxx
SOFA									
Baseline (n=<n>)	xx.x $\pm$ x.x	xx.x $\pm$ x.x	xx.x $\pm$ x.x	xx.x (xx.x to xx.x)	0.xxx				
Day 4 (n=<n>)	xx.x $\pm$ x.x	xx.x $\pm$ x.x	xx.x $\pm$ x.x	xx.x (xx.x to xx.x)	0.xxx	xx.x $\pm$ x.x	xx.x $\pm$ x.x	xx.x (xx.x to xx.x)	0.xxx

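### The primary day-7 OI comparison is in effect limited to patients alive and still ventilated, so it can be biased if aspirin changes death or extubation

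*SAP*

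**What the plan says.** Section 2.1: "The primary outcome measures OI at day 7". The time point is defended with "We have chosen day 7 as we expect this time interval will minimise the competing effects of death and extubation".

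Section 4 defines OI as MAP × FiO2 / PaO2 × 100, in cmH2O/kPa. Section 2.2 sets when measurement stops: "Outcomes will be measured at baseline and daily up to day 14 or until the patient is discharged from ICU or the patient dies".

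Section 6 makes the unadjusted comparison primary ("Unadjusted (primary analysis) and adjusted analysis will be carried out") and names the test: "Unadjusted analysis will be carried out using Independent sample t-test". It also states: "Analyses will be conducted according to intention to treat principle".

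On missing values the SAP speaks in four places:
- Section 3.4 rules out imputation.
- Section 6 allows last value carried forward (LOCF) as a secondary analysis.
- Section 7.4 builds the last available OI before discontinuation into the main endpoint itself.
- Table A3 has a row "Observed values (n=<n>") for the primary outcome and a separate row for LOCF values.

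Section 6 also permits a mixed model for the adjusted analysis, and Table A4 gives its shell.

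**The concern.** The unit of OI shows that MAP is mean airway pressure, so a patient who is extubated or dead at day 7 has no natural OI. Patients at both ends of the outcome range leave the comparison: those well enough to be extubated and those who died. Both exits happen after randomisation, and an effective or harmful drug could alter either.

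If aspirin led to earlier extubation, its mildest cases would be removed and it would look worse than it is. If it increased early death, its sickest cases would be removed and it would look better. What is at stake is the size of the primary estimate and the power to detect it. The SAP names both competing events but relies on the choice of day 7 to keep them small.

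**Working it through.** **1. Who is in the primary test.** Section 3.4 (no imputation), Section 6 (unadjusted t-test, LOCF secondary) and Table A3 (observed row separate from LOCF row) together give an observed-case analysis. Section 2.2 ends measurement at death or ICU discharge. The Section 4 formula needs an airway pressure, so continued ventilation is also required; this last step is an inference, which the SAP does not state.

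**2. The plan's sample size reproduces.** Inputs (Section 5): difference 39, SD 51, 80% power, two-sided 0.05. The standardised effect is 39/51 = 0.765. The two-sample t-test needs 27.8, so 28 per arm, with power 80.2%. Allowing for 5%: 28/0.95 = 29.5, so 30 per arm and 60 in total.

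Section 5 justifies the 5% by withdrawals and loss to follow-up only. With 30 randomised per arm and the same 39 and 51:

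| Share with observed day-7 OI | Patients per arm | Power |
|---|---|---|
| 95% | 28.5 | 80.9% |
| 80% | 24 | 73.7% |
| 70% | 21 | 67.7% |
| 60% | 18 | 60.6% |

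This is loss of numbers alone, before any bias.

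**3. Illustration of selection.** The SAP gives no day-7 death or extubation rates, so these are assumptions:
- Latent day-7 OI is lognormal with mean 62 and SD 51 (Section 5), 30 per arm.
- In placebo, 20% are extubated and 15% dead by day 7, leaving 100 - 20 - 15 = 65% observed.
- Extubation and death follow a multinomial logit on standardised log OI. Low OI favours extubation and high OI favours death, with coefficient 1.0 or 1.5.
- Aspirin multiplies OI: by 23/62 for a mean difference of -39, or by 0.58 for 62 × (0.58 - 1) = -26.

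The power ranges span both coefficients and repeated simulation runs.

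| True OI difference | Observed difference | t-test power, observed cases | Rank composite, all 60 | t-test, complete data |
|---|---|---|---|---|
| -39 | about -33 to -28 | about 75–85% | about 95–98% | above 99% |
| -26 | about -21 to -18 | about 36–44% | about 56–64% | about 73% |

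Power at -39 looks high against the planned 80% because a proportional effect also shrinks the aspirin SD, to 51 × 23/62 = 18.9. The fair comparator is the last column.

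**4. No effect on OI.**
- Death and extubation equal in the two arms: observed difference about 0.
- Death raised from 15% to 25–30% on aspirin: about -4 to -7, a false benefit.
- Extubation raised from 20% to 35–40% on aspirin: about +4 to +7, a false harm.

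In the unequal scenarios the t-test rejects in about 5 to 8% of trials.

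**5. A different selection model.** Here a noisy threshold on OI decides both events (correlation with OI 0.3 to 0.9; placebo 20–30% extubated, 10–15% dead). With no OI effect, 10 to 20 points more extubation and/or 10 points fewer deaths gives +1.8 to +17. Ten points less extubation gives about -2 to -4. A true -39 shrinks to about -33 to -17 (correlation 0.6 to 0.9). The directions agree with steps 3 and 4; the size depends on the assumptions.

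**The case against.** **The plan does not simply drop these patients.** Section 7.4 would keep them through the last available OI, Section 6 plans an LOCF analysis, and a mixed model would use earlier OI values. That is true, and it means the sections conflict on what the primary analysis is. None of these solves the problem. LOCF gives a dead patient and an extubated patient alike an OI from their time on the ventilator. The mixed model is optional, belongs to the adjusted analysis, and treats both events as ordinary missing data.

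**Bias is not shown.** A reader might infer that the primary result is biased. The document does not support that: it gives no event rates, and bias vanishes if aspirin changes neither OI nor either event. A reader might also infer that a real effect could change sign. No scenario above shows this; real effects shrink, and the null shifts are small beside an SD of 51.

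**P/F ratio.** It is tempting to extend the extubation argument to it. Section 4 defines P/F as PaO2/FiO2 without airway pressure, so it is cut off by death and ICU discharge, not by extubation as such. OI at days 4 and 14 does share the problem.

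**Some transparency is planned.** Ventilator-free days, ventilation duration and 28- and 90-day mortality are tabulated by arm, and Table A5 gives the number with airway pressure at day 7. Deaths and extubations by day 7 are not listed, and nothing links these tables to the reading of the primary result.

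**A rank composite as primary would go too far.** It would replace the stated outcome, cut it loose from Section 5, and bring in events the SAP says it is not powered for. This stands, so the composite belongs among the sensitivity analyses.

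**Conclusion.** The concern holds as a risk of bias. On the better-supported reading of Sections 3.4 and 6 and Table A3, the primary test conditions on survival and continued ventilation at day 7. That is not a comparison of all randomised patients, and no planned analysis puts death and extubation in their proper place.

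Under the assumed placebo rates of 20% and 15%, real effects are attenuated by roughly 15 to 30% (from -39 to between -33 and -28: 6/39 = 15% and 11/39 = 28%; from -26 to between -21 and -18: 5/26 = 19% and 8/26 = 31%). Null shifts are about 4 to 7 units in either direction. All of this rests on the assumed rates, the lognormal shape and the assumed strength of the link between OI and each event. Attenuation is most likely when the drug works, because lower OI should bring earlier extubation.

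**What to change.** 1. Keep the day-7 OI mean difference as primary. Reconcile Sections 3.4, 6 and 7.4 so that one primary analysis set and one rule for absent day-7 OI are named.
2. Pre-specify as the key sensitivity analysis a rank composite at day 7 on all randomised patients:
   - best rank: alive and breathing unassisted as Section 4 defines it;
   - middle: alive and on ventilatory support (Section 4 counts non-invasive pressure support here), ranked by OI, using the last available OI if the day-7 value is missing;
   - worst rank: dead.
3. Test it with a Wilcoxon test stratified by vasopressor requirement, the randomisation stratum in Section 7.2. Report the probability of a better outcome with its 95% CI.
4. Add to Table A3, beside the primary result, the numbers by arm who at day 7 are dead, breathing unassisted, and have an observed OI.

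Cost: SAP wording and one more analysis. Section 4 already requires dates of death and of unassisted breathing. Day-7 status should be taken as of that day, because Section 4 dates unassisted breathing from the final ventilation-free period, which a later return to ventilation would move. The drawback is that the composite is not in OI units, so it is read beside the mean difference and does not replace it.

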### **2.2 Secondary outcome measures**

The following secondary clinical outcomes will also be assessed:

1. OI at days 4 and 14
2. Physiological indices of ARDS, as measured by respiratory compliance (CRs) and P/F ratio on days 4, 7 and 14
3. Organ failure as measured by change in sequential organ failure assessment (SOFA) score from baseline to days 4, 7 and 14
4. Safety and tolerability as assessed by the occurrence of adverse events/reactions (AE/AR), serious adverse events/reactions (SAE/SAR) and suspected unexpected serious adverse reactions (SUSAR).

Outcomes will be measured at baseline and daily up to day 14 or until the patient is discharged from ICU or the patient dies. Although duration of ventilation, ventilation free days at day 28 and 28 and 90-day mortality as well as length of ICU stay will be recorded, these important clinical outcomes are not included as major outcome measures as the study is not adequately powered to assess these outcomes.

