## 7.4 Main Clinical Endpoints

- Oxygenation Index (OI) at day 7 or the last available OI prior to patient discontinuation from the study, Mean  $\pm$  SD by treatment arm
- Oxygenation index (OI) at days 4 and 14, Mean  $\pm$  SD by treatment arm
- Respiratory compliance (CRs) at days 4, 7 and 14, Mean  $\pm$  SD by treatment arm
- P/F ratio at days 4, 7 and 14, Mean  $\pm$  SD by treatment arm
- Sequential organ failure assessment (SOFA) score from baseline to day 4, 7, and 14, Mean  $\pm$  SD by treatment arm

Refer to table A 1. Main Clinical Outcome Variables: PF Ratio, Oxygenation Index, SOFA, Respiratory Compliance at each visit

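### SOFA is defined as change from baseline, but the only unadjusted test planned is of the raw score on each day

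*SAP*

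**What the plan says.** Four places in the SAP describe the SOFA outcome.

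- **Section 2.2**, item 3: "Organ failure as measured by change in sequential organ failure assessment (SOFA) score from baseline to days 4, 7 and 14". Items 1 and 2 of the same list (OI, compliance, P/F ratio) are values on a day, so SOFA is the only one defined as a change.
- **Section 6**: "Secondary outcome measures are OI, CRs, PF ratio, and SOFA score at day 4, 7, 14 and safety". It continues "Unadjusted and adjusted analysis will be carried out on OI, CRs, PF ratio, SOFA score", and then "Unadjusted analysis will be carried out using Independent sample t-test". The adjusted analysis is ANCOVA or a mixed model, the choice depending on how much data each time point holds. No covariates are named.
- **Section 7.4**: "Sequential organ failure assessment (SOFA) score from baseline to day 4, 7, and 14", summarised as mean and SD by arm. The word change is absent, and the section then refers by title to the main clinical outcome table.
- **Table A3** in Appendix 1, titled "Main Clinical Outcome Variables: PF Ratio, Oxygenation Index, SOFA, Respiratory Compliance at each visit": SOFA has rows for Baseline, Day 4, Day 7 and Day 14, each with an unadjusted mean difference, confidence interval and p-value. The layout is that used for the outcomes that are not changes, and there is no change row.

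The appendix does label change from baseline elsewhere, in the age and kidney function table, but only for eGFR and creatinine.

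**The concern.** An outcome and its test should concern the same quantity. Here the outcome is a change, while the only test that section 6 names for an unadjusted comparison is applied to the score on the day. An analyst who follows section 6 and fills in Table A3 will report an unadjusted difference, interval and p-value for something other than the outcome in section 2.2.

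A reader cannot reliably recover the change by subtracting the Table A3 means, because the Baseline row and the later rows need not contain the same patients.

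Counting from section 2.2, SOFA supplies three of the eleven secondary efficacy comparisons (OI 2 + compliance 3 + P/F ratio 3 + SOFA 3). At stake are the estimate and the precision reported for those three.

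**Working it through.** **The plan's own figure.** The SAP gives no SD, correlation or power for SOFA. Its only sample size (section 5) is for OI at day 7: difference 39, SD 51, 80% power, two-sided 0.05. A t-test calculation gives 27.84, so 28 per arm, with power 0.802. Allowing 5% drop-out, 56/0.95 = 58.9, so 59, or 60 as an even total. This reproduces the plan and does not depend on how SOFA is defined.

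**Inputs for SOFA.** 28 per arm is taken from section 5. Equal SDs at baseline and follow-up, and a baseline-to-follow-up correlation r, are assumptions, so a range of r is shown.

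**Step 1: difference between the two estimates.** For patients with both values,

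difference in change = difference in day score − difference in baseline score.

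The estimates therefore differ by exactly the observed baseline imbalance. In units of the baseline SD its standard error is √(1/28 + 1/28) = √(2/28) = 0.267. A chance imbalance of up to 1.96 × 0.267 = 0.52 SD in either direction would be unremarkable.

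**Step 2: precision.** Relative to the raw score, the variance of the change is 1 + 1 − 2r = 2(1 − r). With baseline as a covariate, the ANCOVA residual variance is 1 − r².

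For power, take the effect at which the raw-score test has 80% power: (1.960 + 0.842) × 0.267 = 0.75 SD. For relative variance k, power is approximately Φ(2.802/√k − 1.960).

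| Assumed r | Change / raw | ANCOVA / raw | Power, raw | Power, change | Power, ANCOVA |
|---|---|---|---|---|---|
| 0.3 | 1.4 | 0.91 | 80% | 66% | 84% |
| 0.5 | 1.0 | 0.75 | 80% | 80% | 90% |
| 0.7 | 0.6 | 0.51 | 80% | 95% | 97.5% |

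The two t-tests have equal precision only at r = 0.5. ANCOVA is the most precise of the three in every row.

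**Step 3: why a baseline covariate removes the ambiguity.** Subtracting baseline from the response lowers the fitted baseline coefficient by 1 and leaves everything else unchanged. The treatment effect, its standard error and its p-value are therefore the same for change and for raw score.

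One simulated data set illustrates this (28 per arm; baseline mean 9, SD 3; all values invented for the check):

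- raw-score t-test: −0.27, p = 0.69
- change-score t-test: −0.55, p = 0.41
- ANCOVA with baseline, either response: −0.418, standard error 0.577, p = 0.473

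The gap between the t-tests, −0.27 − (−0.55) ≈ 0.27 before rounding, is the baseline imbalance in that sample.

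**Step 4: does the SAP assure that covariate?** It does not. Section 6 says only "Adjusted analysis will be carried out using ANCOVA or" a mixed model. Table A3 leaves the adjusted cells empty in its Baseline rows, which is consistent with baseline being a covariate but does not state it. Table A4, the mixed-model shell, lists group, day and their interaction, with no row for baseline.

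**The case against.** The strongest reply is that this is loose drafting and does little harm. Section 7.4 keeps a baseline-to-day phrasing for SOFA alone, so the authors probably still meant change. The Appendix 1 tables are headed as example drafts. An adjusted analysis is already planned, and with baseline SOFA in it the choice between change and score makes no difference. Under randomisation the two t-tests also have the same expected between-arm difference among all randomised patients.

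Most of this stands, and it limits the point. It does not remove it. Section 6 is the operative analysis text and does not mention change. Section 7.4 refers to a table without a change row. The adjusted analysis is safe only if baseline SOFA is included, which is nowhere stated.

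Three stronger readings are tempting but unsupported:

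- **A reader might infer that the SAP pre-specifies two competing SOFA t-tests.** It does not. Section 2.2 defines an outcome and names no test. The one unadjusted test named is of the score.
- **A reader might infer that the raw-score comparison is biased.** Given the shared expectation just described, the choice affects the estimate obtained, its precision and its p-value. It does not by itself introduce bias.
- **A reader might add that SOFA is recorded only until ICU discharge or death.** That is true, but it applies to every daily outcome, raw or change. It is a separate issue and does not bear on this mismatch.

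**Conclusion.** The mismatch is real and is in the current text. The unadjusted SOFA analysis in section 6 and Table A3 is not an analysis of the outcome defined in section 2.2, and no other section supplies one.

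The difference between the two estimates equals the baseline imbalance whatever the correlation. Its standard error of 0.27 SD assumes 28 patients per arm with data and would be larger with fewer. The variance ratios assume equal variances and an r that the SAP does not give, so they show a range and are not a prediction for this trial. The adjusted analysis can answer the stated question, but only if baseline SOFA is a covariate.

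This is a minor-to-moderate point on a secondary outcome. The primary outcome and the sample size are untouched.

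**What to change.** - **Sections 6 and 7.4:** describe the SOFA outcome as in section 2.2, as change from baseline to days 4, 7 and 14.
- **Table A3:** replace or supplement the SOFA day rows with change-from-baseline rows, so that any unadjusted SOFA test is of the change.
- **Section 6:** state that the SOFA result is interpreted from the ANCOVA or mixed model, with baseline SOFA and the vasopressor stratum as covariates. Section 7.2 gives vasopressor requirement as the stratification factor.

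The unadjusted column may stay once it matches the definition. Dropping its p-values for SOFA alone would be a preference and is not needed to resolve the mismatch.

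The cost is SAP wording and one table shell. No new data are needed, since section 2.2 already has outcomes measured at baseline and daily.
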